2.1 STUDY DESIGN AND TREATMENTS

This is a single-centre, open-label, adaptive, randomised study using the *P. falciparum* induced blood stage malaria (IBSM) inoculum as a model to characterise the safety, tolerability, PK, pharmacodynamic (PD) activity, and PK/PD relationship of combined single dose administration of OZ439 and PQP.

The study was conducted in three cohorts of 8 subjects each using up to 4 different single doses of OZ439 and PQP in each cohort. Subjects were malaria naïve healthy males or females, aged between 18-55 years old, who met all of the inclusion criteria and none of the exclusion criteria.

The first cohort was composed of 4 groups of 2 subjects each. Subjects were randomised into one of 4 dose groups and administered single oral doses of OZ439 and PQP in combination. The combined dose of OZ439 and PQP was different for each of the 4 groups in this cohort as shown in Table 1.

Table 1. OZ439 and PQP Cohort 1 dose groups

Drug	Dose group			
	1A	1B	1C	1D
OZ439 (mg)	200	200	400	400
PQP (mg)	480	640	480	640

The OZ439 and PQP dose levels and the number of subjects per dose for Cohorts 2 and 3 were determined adaptively during the study.

After review of the PK/PD and safety data from Cohort 1 by the Safety and Data Review Team (SDRT) it was determined that cohort 2 would be composed of 2 dose groups of 4 subjects each. Subjects were randomised into one of 2 dose groups and administered single oral doses of OZ439 and PQP in combination. The combined dose of OZ439 and PQP will be different for each dose group in this cohort as shown in Table 2.

Table 2. OZ439 and PQP Cohort 2 dose groups

Drug	Dose group	
	2A	2B
OZ439 (mg)	800	200
PQP (mg)	960	320

A similar analysis was done at the end of Cohort 2 by combining data from cohorts 1 and 2 to decide the doses to be tested in Cohort 3. Two groups of 4 subjects each were considered. Subjects were randomised into one of 2 dose groups and administered single oral doses of OZ439 and PQP in combination as shown in Table 3.

Table 3. OZ439 and PQP Cohort 3 dose groups

Drug	Dose group	
	3A	3B
OZ439 (mg)	400	800
PQP (mg)	640	640

Each subject was inoculated on Day 0 with approximately 2,800 viable parasites of *P. falciparum*-infected human erythrocytes administered intravenously. Subjects were followed up daily via phone call or text message on Days 1 to 3 post-inoculation to solicit any AEs.

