Therefore, the dose group specific PRR (PRR_{48, D}) and corresponding 95% CI is estimated as shown in Equation (4) and (5), respectively:

$$PRR_{48,D} = 10^{-48 \times \bar{\beta}_1} \quad (4)$$

$$95\% \text{ CI: } 10^{-48 \times (\bar{\beta}_1 \pm 1.96 \times SE(\bar{\beta}_1))} \quad (5)$$

Comparison of dose group specific PRR_{48S}

To determine whether there are differences between dose group specific PRR_{48S}, an omnibus test for between dose group differences is used [10]. The test is used to assess whether there are differences in the weighted mean slope of the J doses, using the test statistic shown in Equation (6) at the 5% significance level,

$$Q_B = \sum_{j=1}^J w_j \cdot (\bar{\beta}_j - \bar{\beta}_{..})^2 \sim \chi_{J-1}^2 \quad j = 1, \dots, J \quad (6)$$

The weight for the j^{th} dose is denoted by $w_j = \sum_{i=1}^{s_j} w_{ij}$ for subject i with appropriate overall fit in dose j . The $\bar{\beta}_j$ is the weighted average slope for dose j as defined in Equation (7), and $\bar{\beta}_{..}$ is the weighted grand mean given by:

	STATISTICAL ANALYSIS PLAN	QP17C19
		Page 34 of 53

$$\bar{\beta}_{..} = \frac{\sum_{j=1}^J w_j \bar{\beta}_j}{\sum_{j=1}^J w_j} \quad (7)$$

Interim analyses of comparisons between dose-group specific PRR_{48S} will first be performed for all dose groups within each cohort. Final analyses will include the comparison between the dose groups 1D vs. 3A, each receiving the same dose combination (OZ439 400 mg, PQP 640 mg). Final analyses will be performed based on the factorial design of the study, for the following dose groups to assess differences in increasing PQP dose with constant 200 mg dose of OZ439 (1A vs. 1B vs. 2B), 400 mg dose of OZ439 (1C vs. 1D/3A) and 800 mg dose of OZ439 (2A vs. 3B). Similarly, comparisons will be made to assess differences between dose groups with increasing OZ439 dose with constant 480 mg dose of PQP (1A vs. 1C) and 640 mg dose of PQP (1B vs. 1D/3A vs. 3B). Type 1 error corrections will not be performed as analyses was implicit by the study design.

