Model evaluation

Assessment of model adequacy and decisions about increasing model complexity will be driven by the data and guided by goodness-of-fit criteria, including

1. visual inspection of diagnostic scatter plots (observed vs. predicted concentration, residual/weighted residual vs. predicted concentration or time and histograms of individual random effects, for example),
2. successful convergence of the minimization routine with at least 2 significant digits in parameter estimates,
3. plausibility of parameter estimates,
4. precision of parameter estimates,
5. correlation between model parameter estimation errors < 0.95, and
6. the Bayesian information criterion, given the minimum objective function value and number of estimated parameters.

For the nonlinear fixed effects models, additional diagnostic plots will be produced:

7. objective function values across multiple fits from randomised initial guesses, and

	
STATISTICAL ANALYSIS PLAN
	
QP17C19

		
Page 40 of 53

8. profile likelihood plots

All parameter estimates will be reported with a measure of estimation uncertainty, such as the standard error of the estimates. The individual PK fits will be used to evaluate the adequacy to use the individual PK parameter estimates as regression parameters for PD modelling.

The adequacy of simulation with the final models will be evaluated by visual predictive checks. Visual predictive checks for each dose level will be performed by simulation of the study 200 times taking parameter estimation uncertainty into account. 95%-confidence intervals for the 5th percentile, the median, and the 95th percentile will be derived and compared to the corresponding values based on the data.

To compare simulations of the final model with patient data, both, the data and the simulation will be transformed into a life table format indicating for each individual the time of recrudescence, i.e., the time at which parasite levels re-occur after being BLQ or the time for which parasitaemia levels are minimum, or, if not defined, the last observed time point without recrudescence. The Kaplan-Meier estimator [KAP58, THE15, TER00] will be used to compare model and data.

PK modelling

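### The per-dose-level visual predictive checks, with 2 to 6 subjects per dose combination, would rarely reveal overstated between-subject variability; a pooled prediction-corrected check should be added

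*SAP*

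**What the plan says.** SAP 9.4, under model evaluation, gives these plots a specific job: "The adequacy of simulation with the final models will be evaluated by visual predictive checks". They are stratified: "Visual predictive checks for each dose level will be performed by simulation of the study 200 times taking parameter estimation uncertainty into account". The statistics are then named: "95%-confidence intervals for the 5th percentile, the median, and the 95th percentile will be derived and compared to the corresponding values based on the data". No pooled or prediction-corrected version is planned, and no rule says what counts as agreement. The planned figures in SAP Appendix 3 do not list a visual predictive check.

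The group sizes are in SAP 2.1. For Cohort 1, "The first cohort was composed of 4 groups of 2 subjects each"; then "cohort 2 would be composed of 2 dose groups of 4 subjects each"; and for Cohort 3, "Two groups of 4 subjects each were considered". Groups 1D and 3A received the same combination, as SAP 8.4 notes.

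Other adequacy criteria stand beside this one: "Assessment of model adequacy and decisions about increasing model complexity will be driven by the data and guided by goodness-of-fit criteria". They include residual plots, histograms of individual random effects, precision of estimates and the Bayesian information criterion. The fixed-effects fits add randomised-start and profile-likelihood checks, and there is a Kaplan-Meier comparison with patient data.

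**The concern.** A 5th or 95th percentile taken from two, four or six subjects is an interpolation next to the smallest or largest value, so it says little about the tails. The tails matter here. In step 5 of the model building (SAP 9.4), the inter-individual variability of Emax and EC50 in the combination model is fixed at the monotherapy values. The patient simulations then draw individual parameters from the variability estimated in Monolix to predict ACPR28. Whether the carried-over variability fits the combination subjects is therefore an open question.

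If the spread is too wide, too many simulated patients land in both tails, and the predicted share with recrudescence moves accordingly. If the prediction then disagrees with the Phase 2 result, a weak earlier check leaves it unclear whether the variability was wrong or the challenge model does not predict.

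**Working it through.** **Plan's own figure.** The documents give no error rate or sensitivity for this check, so there is none to reproduce.

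**Inputs from the documents (SAP 2.1, 2.4, 8.4, 9.4).** Dose groups: 2+2+2+2+4+4+4+4 = 24, the stated total.
- By combination, with 1D and 3A joined (2+4 = 6): 2, 2, 2, 4, 4, 4, 6.
- By OZ439 dose: 200 mg 2+2+4 = 8; 400 mg 2+2+4 = 8; 800 mg 4+4 = 8.
- By PQP dose: 320 mg 4; 480 mg 2+2 = 4; 640 mg 2+2+4+4 = 12; 960 mg 4.

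The single-drug reading is possible because SAP Section 5 defines a dose group as a combination of single dose levels. Monotherapy subjects would add to those panels, but their numbers are not given.

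**Assumptions (not in the documents).** One time point, normal log-scale data, model SD 1, no values below the quantification limit, no loss after rescue. The size of error examined is a factor of 2 in SD.

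**How far the tails are observed.** P(smallest value lies below the true 5th percentile) = 1 − 0.95ⁿ: 9.8% at n=2, 18.5% at n=4, 26.5% at n=6. It first reaches 95% at n=59.

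**Per-panel behaviour.** The 95% limits of each sample percentile came from 200,000 simulated panels of the same n; 40,000 observed panels were then drawn. A panel passes if all three percentiles lie inside their limits.

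| n | Correct model: flags | Model SD 2x too large: passes | Model SD 2x too small: passes |
|---|---|---|---|
| 2 | 9% | 99.9% | 48% |
| 4 | 12% | 98.7% | 31% |
| 6 | 13% | 94% | 21% |
| 8 | 13% | 85% | 15% |
| 12 | 13% | 58% | 7% |
| 24 | 14% | 13% | 2% |

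**Whole panel set.** Panels contain different subjects, so pass rates multiply.
- SD too large, seven combinations: 0.999³ × 0.987³ × 0.94 ≈ 0.90. With 1D and 3A kept apart: 0.999⁴ × 0.987⁴ ≈ 0.945.
- SD too large, OZ439 panels: 0.846³ ≈ 0.60. PQP panels: 0.987³ × 0.58 ≈ 0.56. Pooled, n=24: 0.13.
- SD too small, seven combinations: 0.48³ × 0.31³ × 0.21 ≈ 0.0007, about 0.1%.
- Correct model, seven combinations: 1 − 0.906³ × 0.876³ × 0.871 ≈ 0.565, about 57%. Pooled: about 14%.

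**Sensitivity.** With 20% log-scale uncertainty on the model SD (the SAP includes parameter uncertainty, of unstated size):
- SD too large: all seven panels pass 90% of the time, against 28% pooled (1 − 0.72).
- Correct model: at least one of seven flags 47% of the time (1 − 0.532), against 7% pooled.

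The SAP's 200 simulated studies make the limits themselves noisy. Rerun with limits from 200 draws (4,000 repetitions), without parameter uncertainty:
- SD too large: all pass 84% (combinations), 51% (OZ439) and 49% (PQP), against 11% pooled.
- Correct model: at least one of seven flags 63%, against 16% pooled.

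The contrast remains in both.

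**The case against.** A reader might infer that a model with variability wrong by a factor of 2 in either direction would usually pass. The documents do not support that. The plan compares three percentiles in every panel, and with an SD twice too small the full set of seven almost never passes. Quoting the flag rate of one percentile in one small panel against a pooled panel of 24 would also be an unequal comparison, because the planned set uses the same 24 subjects. The figures above compare whole sets.

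A reader might also infer that these plots alone decide whether the model is adequate. They do not. SAP 9.4 lists other criteria, the random-effect histograms bear on variability directly, and the comparison of simulated with observed ACPR28 tests the Phase 2 prediction itself. Nor are the limits biased: simulated and observed panels have the same n, so each percentile's interval is calibrated. The weakness is low sensitivity in one direction.

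Three further points stand. The 2-to-6 count depends on reading a dose level as a combination. The variability of Emax and EC50 comes from monotherapy studies whose group sizes are not given, so the sensitivity of checks on those data cannot be computed. And the pooled figure is optimistic at late times: SAP 9.3 removes parasite data after rescue, so fewer than 24 subjects may remain. At n=12 the pass rate for an overstated SD is 58%.

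What survives is that the planned set seldom detects overstated variability, and that its flags are hard to interpret without a stated rule.

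**Conclusion.** The point holds as a cheap improvement, not as a flaw that undermines the analysis. On dose combinations, the per-dose-level panels miss a twofold overstatement of SD about 90% of the time; on the single-drug readings they miss it about 60% (OZ439) or 56% (PQP) of the time; one pooled panel misses it about 13%. They do detect a twofold understatement. Even so, at least one of seven panels flags about 57% of the time under a correct model, against about 14% pooled, so one flagged panel says little.

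These figures rest on one time point, normal log-scale data, no censoring at the quantification limit, no rescue dropout, and a factor-of-2 error chosen for illustration. Several correlated time points per subject were not modelled; they would be expected to raise flag rates under both a correct and an understated model.

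**What to change.** In SAP 9.4, model evaluation, add a prediction-corrected visual predictive check that pools the 24 combination subjects, plus one for each monotherapy study, and name it as the main percentile comparison, with the same three percentiles and 95% intervals. Keep the dose-level plots, but show individual observed profiles over the simulated 90% prediction interval, without percentile comparison. Say whether a dose level means a combination or a single-drug dose. State beforehand how an excursion will be read, since even the pooled panel flags about 14% of the time under a correct model. Show the number of subjects contributing at each time, and list the figure in SAP Appendix 3.

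The cost is a few lines of code on simulations already planned; no new data and no change in conduct are needed. The drawback is that pooling can mask a misfit confined to one dose group, which is what the retained dose-level overlays are for.

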### 10.3.2 ANALYSIS OF THE PRIMARY EFFICACY ENDPOINT(S)

A model-based analysis is foreseen to characterise the PK/PD relationship between OZ439 and PQP plasma concentrations and blood stage asexual parasitaemia. For assessing the contribution of each compound and their interaction effect, data of this combination therapy study, will be pooled with data from previous human challenge monotherapy studies for each compound, i.e. QP12C01 (OZ439) and QP13C05 (Piperaquine).

The final PK/PD model will describe the time courses of plasma concentrations and of the parasite counts by a nonlinear mixed effects (NLME) modelling approach. The change in parasite count will be modelled as the joint effects of parasite growth and drug concentration.

The model will be developed in step wise manner. First, a joint PK model for OZ439 and piperaquine will be established potentially taking PK drug-drug interaction into account. Second, the PD model will be developed using individual PK parameters as regressors. The effect of each compound on parasite clearance is described by a sigmoidal Emax model or related models. Intake into account time delays of the drug action if appropriate. Interactions between OZ439 and PQP will be described using the Generalized PD Interaction (GPD I) model. PD interaction scenarios to be tested with the GLDI model include a change in each drug's EC50, Emax or EC50 and Emax caused by the other drug.

Graphical displays will be given, where appropriate. Details of the modelling analysis will be described in the modelling analysis plan (MAP).

---

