#### PK parameters

Estimation of OZ439 and PQP PK parameters over 28 days after administration of single doses using non-compartmental methods:

The following pharmacokinetic parameters will be determined using non-compartmental methods from plasma concentration-time data from all cohorts: AUC0-168h, AUClast, AUC0-inf, Cmax, tmax, t1/2, tlag, C168h, CL/F, Vz/F and λinf. These data will be summarized descriptively by treatment and dose.

For calculation of descriptive statistics of blood concentrations, values below the LLOQ will be set to zero.

Pharmacokinetic parameters will be determined using STATA® (version 14.0 or higher).

PD parameters

Parasite Reduction Ratio (PRR). The PRR of asexual parasites will be based on the decay of parasitaemia after drug treatment determined by malaria 18S qPCR. The PRR for asexual parasites will be estimated using the slope of the optimal fit of the log-linear relationship of the parasitaemia decay [45]. The optimal fit can be derived using summarised replicate parasitaemia data, which have been cleaned by dealing with potential outliers, values below the limit of detection and non detectable values (ND). The optimal fit of the log-linear parasitaemia-time relationship is determined by using left and right censoring to systematically remove the potential lag phase and tail phase of the parasitaemia decay. The decay rate, estimated slope coefficient from the log-linear decay regression of qPCR data, will be calculated for each subject. The overall cohort dose specific PRR will be estimated with its 95% CI by calculating the weighted average slope estimate and corresponding standard error (SE) using an inverse variance method. Only subjects who have optimal regression models with appropriate fit contribute toward the dose specific PRR. Details are presented in the SAP.

Parasite clearance half-life ( $t_{1/2}$ ). The  $t_{1/2}$  will be derived from the optimal decay rate. Details regarding the calculation will be in the SAP.

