A regression modelling method, to incorporate both left and right censoring to remove potential lag and tail phases of the parasitaemia decay curve in a systematic way, will be used to determine the optimal number of data-points required to calculate the slope (β_1) of the log-linear parasitemia decay. A minimum number of 4 timepoints will be required for regression modelling. If fewer than 4 timepoints are used or if the adequacy of the fit to the data is not sufficient (based on the overall model R² p value ≥ 0.001), the slope and derived parameters will be reported as missing.

The individual PRR₄₈ standardised to 48 hours will be derived from the regression modelling versus time in hours as

$$PRR_{48} = 10^{-48 \times \beta_1} \quad (1)$$

The parasite clearance half-life is the transformation of the slope coefficient (per time, equivalent to PRR₄₈) into a time period. The relationship between PRR₄₈ and parasite clearance half-life is a simple transformation of the PRR₄₈, as shown in Equation (2):

$$t_{1/2} = \log_{10}(2) \times \left(\frac{48 \text{ hours}}{\log_{10}(PRR_{48})} \right) = \frac{\log_{10}(2)}{-\beta_1} \quad (2)$$

where the PRR₄₈ is the parasitaemia ratio estimated over a 48 h interval that is subsequently transformed into a per hour clearance rate.

	STATISTICAL ANALYSIS PLAN	QP17C19
		Page 33 of 53

Individual regression plots of parasitaemia over time after treatment will be produced. Data listings of PRR₄₈ and PC_{t1/2} will show the first, last time point and the number of time points used in the regression model.

Weighted mean of regression coefficient (95% CI) of PD endpoints (log₁₀-(Parasitemia) and PC_{t1/2} by dose group) will be plotted by dose group.

Estimating dose group specific PRR (PRR_{48, D})

Of the s subjects with appropriate overall fit ($p < 0.001$), the average PRR₄₈ and corresponding 95% CI for each dose group is estimated by using the inverse variance method [9] to calculate the weighted average linear regression slope ($\bar{\beta}_1$) and corresponding SE. The weighted average slope for s subjects in the dose with appropriate overall fit is given by Equation (3):

$$\bar{\beta}_1 = \frac{\sum_{i=1}^s (w_i \times \beta_{1,i})}{\sum_{i=1}^s w_i}, \quad i = 1, \dots, \quad (3)$$

where the weight is the inverse of the squared SE, $w_i = \frac{1}{SE(\beta_{1,i})^2}$. The SE of $\bar{\beta}_1$ is estimated

$$as, SE(\bar{\beta}_1) = \sqrt{\frac{1}{\sum_{i=1}^s w_i}}.$$

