9.4 METHODS

Model building

General PKPD model building approach

Population models of the PK and PD will be developed in step-wise manner.

1. An NLME model for the PK (OZ439, PQP and combinations) will be developed to obtain individual PK parameter estimates based on which the individual PK profiles are described well.
2. The PKPD population model for OZ439 mono treatment will be built sequentially. That is, a PK model will be developed first. Second, using the individual PK parameter estimates as regression parameters and estimating the PD part of the model only. Estimation of typical and individual PD parameters will first be performed with IQRtools SysFit to investigate model identifiability and second with Monolix to additionally estimate inter-individual variability (IIV).
3. The PKPD population model for PQP mono treatment will be built using the individual PK parameter estimates as regression parameters and estimating the PD part of the model only. Estimation of typical and individual PD parameters will first be performed with IQRtools SysFit to investigate model identifiability and second with Monolix to additionally estimate IIV.
4. The parasitaemia base line levels and parasite growth rate (PD parameters) in the absence of the drug will be estimated from the total parasite counts of the OZ439/PQP combo study QP17C19 before treatment. Estimation of typical and individual PD parameters will be performed with IQRtools SysFit.
5. The PKPD model for the OZ439/PQP combo study will be built using the
 - individual PK parameter estimates as regression parameters,
 - individual growth rate and base line parasitaemia values as regression parameters,
 - typical E_{max} , EC50 and Hill parameter values of OZ439 and PQP as fixed parameters from the mono PD models (Monolix),
 - IIV values for and E_{max} , EC50 of OZ439 and PQP as fixed parameters from the mono PD models (Monolix).
 - Individual PD parameters and drug-drug interaction parameters will first be estimated using IQRtools SysFit to investigate identifiability of multiple drug-drug interaction models. Second, considering the identifiability analysis, Monolix will be used to estimate individual parameters for selected models.

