where $PL = \ln(P)$ is the log-transformed parasite counts. The killing rate $Kill = Kill_1 + Kill_2$ is composed of contribution from OZ439 (index 1) and PQP (index 2). The killing rate of each drug is described by an E_{max} model. The E_{max} model assumes a direct effect of concentrations on parasite killing/clearance, such as:

$$Kill_1 = EMAX_1 \cdot \frac{Cc_1^{Hill_1}}{Cc_1^{Hill_1} + EC50_1^{Hill_1}}$$

$$Kill_2 = EMAX_2 \cdot \frac{Cc_2^{Hill_2}}{Cc_2^{Hill_2} + EC50_2^{Hill_2}}$$

Here, Cc is the concentration in the central compartment, $EMAX$ is the maximum effect of the drug, $EC50$ is the concentration that results in 50% of the maximum effect and $Hill$ is the Hill coefficient.

Two alternative models to combine the killing effect of each drug are considered. First, a so-called empirical Bliss independence approach is applied. The kill is modelled as sum of the single effects and an interaction term that is the scaled product of the single effect and an interaction coefficient γ .

$$Kill = Kill_1 + Kill_2 + \gamma \cdot \frac{Cc_1^{Hill_1}}{Cc_1^{Hill_1} + EC50_1^{Hill_1}} \frac{Cc_2^{Hill_2}}{Cc_2^{Hill_2} + EC50_2^{Hill_2}} \min(Kill_1, Kill_2)$$

Second, an additive effect of both drugs on the killing rate is assured, $Kill = Kill_1 + Kill_2$. However, the E_{max} and $EC50$ values employed in the killing contributions can be affected by the other drug. In the analysis, two drug-drug interaction models will be used to describe the effect one drug exerts on the $EC50$ and E_{max} of the other drug: a mutual and a non-mutual model.

	STATISTICAL ANALYSIS PLAN	QP17C19
		Page 42 of 53

The non-mutual model states that

$$\begin{aligned}
 EC50_1^* &= EC50_1 \left(1 + (e^{-\alpha_{21}} - 1) \frac{C C_2^{Hill_2}}{EC50_2^{Hill_2} + C C_2^{Hill_2}} \right) \\
 EC50_2^* &= EC50_2 \left(1 + (e^{-\alpha_{12}} - 1) \frac{C C_1^{Hill_1}}{EC50_1^{Hill_1} + C C_1^{Hill_1}} \right) \\
 EMAX_1^* &= EMAX_1 \left(1 + (e^{\beta_{21}} - 1) \frac{C C_2^{Hill_2}}{EC50_2^{Hill_2} + C C_2^{Hill_2}} \right) \\
 EMAX_2^* &= EMAX_2 \left(1 + (e^{\beta_{12}} - 1) \frac{C C_1^{Hill_1}}{EC50_1^{Hill_1} + C C_1^{Hill_1}} \right).
 \end{aligned}$$

Hence, the modified EC50 or E_{max} for one drug is the original value scaled by a factor that is modulated by the other drug concentration. In short, $\alpha \geq 0$ decreases the EC50 and $\beta \geq 0$ increases the E_{max} .

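### SAP 9.4 specifies only a direct-effect Emax model and drops, without a stated reason, the protocol's conditional provision for delayed drug action; an unmodelled delay could be partly read as a drug interaction, which is the primary endpoint.

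*SAP*

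**What the plan says.** Protocol 10.3.2 plans a sigmoidal Emax model or a related one for each drug, taking "into account time delays of the drug action if appropriate". It leaves modelling details to a separate modelling analysis plan, which is not among the documents.

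SAP 1.1 lists the PKPD modelling within its own scope and says that it supersedes the protocol where the two differ. SAP 9.4 (PD modelling) states that the Emax "model assumes a direct effect of concentrations on parasite killing/clearance". The driver of killing, Cc, "is the concentration in the central compartment". The alternatives it lists concern only how the two drugs combine: an empirical Bliss term (gamma), or mutual and non-mutual effects of one drug on the other's EC50 and Emax (alpha and beta). No effect compartment, lag or turnover term is named. By contrast, the PK modelling text does list structural features to be tested, such as number of compartments, type of elimination and absorption kinetics.

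SAP 8.4 derives the parasite clearance rate from the same parasitaemia data by a regression designed "to incorporate both left and right censoring to remove potential lag and tail phases of the parasitaemia decay curve in a systematic way". Protocol 10.3.3 has the matching provision, to "systematically remove the potential lag phase and tail phase of the parasitaemia decay".

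In SAP 9.4, step 5 takes typical Emax, EC50 and Hill, and the inter-individual variability of Emax and EC50, as fixed from the monotherapy models. Individual growth rate and baseline enter as regressors. The interaction parameters and individual PD parameters are then estimated.

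**The concern.** The primary PK/PD endpoint is the effect of each drug on the Emax and EC50 of the other. Under the SAP's sequence, the monotherapy models are settled first and the interaction terms are estimated on what those models fail to explain in the combination data. If killing lags behind plasma concentration and the model has no delay, the monotherapy fits absorb the lag only in part, mainly by lowering Emax. What remains appears in the combination data, where the interaction parameters are among the few terms still free. A timing error could then present itself as antagonism or synergy. The secondary endpoint is protected by trimming a lag if there is one; the primary model has no named counterpart.

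**Working it through.** The documents give no figure on this point, so there is nothing to reproduce. The check is first a hand calculation of the mechanism, then simulation of the SAP sequence.

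**Hand calculation (pure lag, saturating concentrations).** Assumed: growth GR = 0.05 per h, OZ439 Emax 0.25 per h, PQP Emax 0.22 per h, baseline 10,000/mL. From SAP 9.3: LLOQ 10/mL. The fall to LLOQ is ln(1000) = 6.908. With true kill rate K and lag L, the time to LLOQ is T = (6.908 + K·L)/(K − GR). A direct-effect reading of the average slope gives K_app = GR + 6.908/T. The combination is truly additive, K = 0.47.

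For L = 4 h:
- OZ439: T = 7.908/0.20 = 39.5 h, K_app = 0.225
- PQP: T = 7.788/0.17 = 45.8 h, K_app = 0.201
- Combination: T = 8.788/0.42 = 20.9 h, K_app = 0.380
- Sum of the two monotherapy values = 0.4255; ratio = 0.380/0.4255 = 0.89

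The same steps give 1.00 at L = 0, 0.94 at 2 h and 0.82 at 8 h. The lag takes a larger share of the shorter combination window, so the monotherapy fits cannot absorb all of it.

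**Simulation of the SAP sequence.** Noise-free, additive killing, no interaction. Direct-effect Emax, EC50 and Hill were fitted to monotherapy data and then fixed. The mutual alpha/beta model and, separately, gamma were then fitted to the seven combination doses, weighted by group size, with growth and baseline fixed.
- From the documents: combination doses and group sizes, inpatient qPCR times (4 to 72 h), LLOQ, the 5,000/mL rescue level and the half-life ranges.
- Assumed: all other PK values, the PD values above with EC50 0.006 (OZ439) and 0.012 (PQP) and Hill 3, and monotherapy doses of 100, 200, 500 mg (OZ439) and 320, 640, 960 mg (PQP).

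The Emax factor is exp(beta) and the EC50 factor is exp(−alpha); truth is 1 for both and 0 for gamma.

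| Delay, both drugs | alpha | beta | Emax factor | EC50 factor | gamma |
|---|---|---|---|---|---|
| None | 0 | 0 | 1.00 | 1.00 | 0 |
| Lag 2 h | −0.98 | −0.07 | 0.93 | 2.66 | −0.19 |
| Lag 4 h | −0.94 | −0.16 | 0.86 | 2.56 | −0.34 |
| Lag 8 h | −0.74 | −0.28 | 0.75 | 2.10 | −0.55 |
| Lag 12 h | −0.51 | −0.37 | 0.69 | 1.67 | −0.68 |
| Effect compartment, ke0 0.5 per h | −0.74 | +0.002 | 1.00 | 2.09 | −0.03 |
| Effect compartment, ke0 0.05 per h | −1.00 | −0.04 | 0.96 | 2.71 | −0.18 |

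Factors use the unrounded estimates. The two ke0 values are half-times of ln2/0.5 = 1.4 h and ln2/0.05 = 13.9 h.

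At a 4 h lag the monotherapy fits take up part of the delay: OZ439 Emax falls from 0.25 to 0.215, that is 14%. Monotherapy RMSE is 0.24 to 0.29 ln units. Adding alpha and beta cuts the combination sum of squares from 159.5 to 69.1, so some misfit remains. In the effect-compartment runs the sums of squares are small throughout (1.1 to 0.2 at ke0 0.5; 26.9 to 8.8 at ke0 0.05). In every run with a lag on OZ439, its fitted Hill ran to the upper bound of 10.

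**Sensitivity to assumptions.** Two further noise-free illustrations used other assumed parameter sets and effect delays with half-times of 2 h (OZ439) and 6 h (PQP).
- 14 sets: median Emax factor 0.81 (range 0.68 to 0.87), EC50 factor 0.81 (0.05 to 1.13).
- 8 sets: median Emax factor 0.93 (0.86 to 1.36), EC50 factor 0.36 (0.05 to 1.12, the lower end at the fitting bound).

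The table's EC50 factors with a delay all lie above 1, while these medians lie below 1, so the EC50 direction is not stable.

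**The case against.** The protocol's provision is conditional, so starting from a direct-effect model does not contradict it. SAP 8.4 and Protocol 10.3.3 speak of a potential lag; the trimming is a general algorithm and does not say that a lag is expected for these drugs. SAP 9.4 offers its equations as a general concept, and its model evaluation text lets the data drive added complexity, with BIC, plausibility of estimates, residuals against time and visual predictive checks. A plot of weighted residuals over time is planned (Figure 14.2.3.3), and a Hill estimate running to a bound would itself be a warning. Step 5 also estimates individual PD parameters, which the simulations leave out and which would take up some of the misfit. The separate modelling analysis plan may cover delay.

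All of this stands, and it limits the point. It does not remove it. The evaluation criteria are generic: they name no delayed-effect alternative and do not require the question to be settled before Emax, EC50 and Hill are fixed. If it is not settled there, the BIC at step 5 compares interaction forms with one another and can favour a spurious one. The SAP text does not refer to the modelling analysis plan.

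**Conclusion.** The SAP narrows the protocol's conditional provision to a direct-effect model without explanation, and its sequential fixing leaves the primary interaction parameters exposed if a delay exists. Under assumed values the spurious interaction ranges from negligible (Emax factor 1.00, with little misfit to explain) to material (0.69 at a 12 h lag on both drugs). These figures show that the leak is possible; they are not an expected effect size.

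A reader might infer more than the documents support:
- That the protocol commits to a delay model: it does so only if appropriate.
- That the SAP itself expects a lag: it allows for a potential one.
- That any lag will be read as an interaction: monotherapy parameters, individual PD parameters and residual misfit absorb part of it, and the listed diagnostics might or might not catch the rest.
- That the ACPR28 predictions are biased by a known amount: the fitted PD parameters feed those predictions, but no effect on ACPR28 has been calculated.

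**What to change.** In SAP 9.4, steps 2 and 3, fit each monotherapy PD model both as direct effect and with a delay (an effect compartment, or a lag or turnover term). Select between them by the BIC and residual-versus-time diagnostics already listed under model evaluation, before any parameter is fixed. Carry the selected structure into step 5, and report the interaction parameters under both structures as a sensitivity analysis.

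The cost is SAP wording and a few extra model runs, with no new data. If a delay is retained, there is one extra parameter per drug and slightly wider intervals.
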